## **4 ADVERSE EVENTS**

### **4.1 Warnings/Precautions**

For complete information on IGSC 20% or IGIV-C 10%, refer to their respective IBs.

## 4.2 Adverse Event Monitoring

Subjects must be carefully monitored for AEs. This monitoring includes clinical and laboratory tests and physical signs. Adverse events should be assessed in terms of their seriousness, severity, and causal relationship to the IP/study drug.

## 4.3 Adverse Event Definitions

### 4.3.1 Adverse Events

An AE is defined as any untoward medical occurrence in a subject or clinical investigation subject administered a medicinal product or study treatment and that does not necessarily have a causal relationship with this treatment. An AE can therefore be any unfavorable and unintended sign (including any abnormal laboratory finding), symptom, or disease temporally associated with the use of a medicinal product, whether or not considered related to the medicinal product.

Any AE that occurs at any time between the signature of the ICF and last day of the subject's participation in the clinical trial must be reported and recorded in the AE eCRF.

All infusion site reactions will be recorded. For the subset of local infusion site reactions where the symptoms/signs lead to infusion interruption or discontinuation, require concomitant medication, or have an impact on the general condition of the subject as judged by the Investigator, these will be considered as AEs.

### 4.3.2 Suspected Adverse Drug Reactions/Adverse Reactions

All noxious and unintended responses to a medicinal product or study treatment related to any dose should be considered suspected ADRs. The phrase “responses to a medicinal product” means that a causal relationship between a medicinal product or study treatment and an AE is at least a reasonable possibility, that is, the relationship cannot be ruled out. In the framework of this study, a suspected ADR with a causal relationship of “definite” will be labeled as an AR; thus, ARs are a subset of suspected ADRs.

The Sponsor is responsible for assessing the suspected ADR expectedness during the clinical trial.

### 4.3.3 Causality of Adverse Event

The Investigator is required to provide a causality assessment for each AE reported to the Sponsor. The Sponsor will consider the Investigator's causality assessment. Assessment of the causal relationship to the study drug will be made according to the following classifications based on Karch FE et al. (39):

**Definite:** An event that follows a reasonable temporal sequence from administration of the treatment or in which the treatment level has been established in body fluids or tissues; and that is confirmed by improvement on stopping the treatment (dechallenge), and reappearance of the event on repeated exposure (rechallenge).

**Probable:** An event that follows a reasonable temporal sequence from administration of the treatment; that is confirmed by dechallenge; and that could not be reasonably explained by the known characteristics of the subject’s clinical state.

**Possible:** An event that follows a reasonable temporal sequence from administration of the treatment but that could have been produced by the subject’s clinical state or other modes of therapy administered to the subject.

**Doubtful/Unlikely:** An event that follows a reasonable temporal sequence from administration of the treatment; but that could not be reasonably explained by the known characteristics of the subject’s clinical state.

**Unrelated:** Any event that does not meet the criteria above.

The operational tool to decide the AE causal relationship is based on algorithms by Karch FE et al. and Naranjo CA et al. (40,41).

When an AE is classified, assessing causal relationship by the Investigator, as definitive, ie, “probable”, “possible” or “doubtful/unlikely”, the event will be defined as a suspected ADR. A suspected ADR with a causal relationship of “definite” will be defined as an AR. When the causal relationship is labeled “unrelated”, then it will be considered that the AE is not imputable to the study treatment and it is not a suspected ADR.

In addition, when a causal relationship between the study treatment and the AE cannot be ruled out by the Investigator and/or Sponsor, it means that the AE cannot be labeled “unrelated”.

For any subject, all AEs that occur at any time from the beginning of IP/study drug administration until the final visit of the clinical trial will be considered as treatment emergent AEs (TEAEs).

For AEs that occur during infusions, the infusion rate in effect at the time of onset of the AE, the time of onset of the AE and the time of AE change materially in intensity and/or resolve will be captured.

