#### **STOPPING RULES FOR THE STUDY AS A WHOLE:**

As a conservative measure, if 5 subjects on IGSC 20% develop an SAE of exactly the same type (ie, the same MedDRA [Medical Dictionary for Regulatory Activities] preferred term) which is not an infection or manifestation of an underlying disorder documented in medical history, then this would constitute an unanticipated clustering which could signal a potential safety concern. If this situation were to arise, the Sponsor will constitute a Safety Review Committee (SRC) whose members (from Grifols) will be impartial and independent of the clinical trial team. In cases where there is a clear medical plausibility supporting an uncommon clustering of SAEs of the same type (not including infections), and these sentinel SAEs are designated as ‘definitely related’, ‘probably related’, or ‘possibly related’ by both the Investigator and the SRC, consideration would be given to possibly discontinuing the study.

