#### 4.3.6 Seriousness of Adverse Event or Suspected Adverse Drug Reaction; Serious Adverse Event

An AE or suspected ADR is considered “serious” if, in the view of either the Investigator or Sponsor, it results in any of the following outcomes:

1. Death
2. Life-threatening AE (life-threatening in the definition of “serious” refers to an event in which the subject was at risk of death at the time of the event; it does not refer to an event which hypothetically might have caused death if it were more severe)
3. In-patient hospitalization or prolongation of existing hospitalization
4. A persistent or significant incapacity or substantial disruption of the ability to conduct normal life functions
5. A congenital anomaly/birth defect
6. An important medical event (important medical event in the definition of “serious” refers to those events which may not be immediately life-threatening, or result in death, or hospitalization, but from medical and scientific judgment may jeopardize the subject or/and may require medical or surgical intervention to prevent one of the other outcomes listed above).

This definition permits either the Sponsor or the Investigator to decide whether an event is “serious”. If either the Sponsor or the Investigator believes that the event is serious, the event must be considered “serious” and evaluated by the Sponsor for expedited reporting.

A distinction should be drawn between serious and severe AEs. The term “severe” is used to describe the intensity (severity) of a specific event; the event itself, however, may be of relative minor medical significance (such as severe headache). This is not the same as “serious”, which is defined on subject/event outcome or action criteria usually associated

with events that pose a threat to a subject's life or functioning. Seriousness (not severity) is a medical term while severity is a subjective term.

According to the medical criteria, an AE or a suspected ADR can be classified as serious, although it does not fulfill the conditions fixed in this section, if it is considered important from a medical point of view.

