#### 4.3.7 Adverse Event and Pregnancy Documentation

All AEs and SAEs occurring after the subject has signed the ICF through the Final Visit (ie, end of study) must be fully recorded in the subject's eCRF or SAE form and medical record. If no AE has occurred during the study period, this should also be indicated in the eCRF.

It is the responsibility of the Investigator to ensure that AEs are appropriately recorded.

At each visit, AEs will be elicited by asking the individual a non-leading question such as "Do you feel different in any way since the last visit?" Moreover, AEs will also be collected through directly observed events or spontaneously volunteered by the subject. Clearly related signs, symptoms and abnormal diagnostic procedures should preferably be grouped together and recorded as a single diagnosis or syndrome wherever possible.

The following variables must be recorded in the AE eCRF:

1. the verbatim term (a diagnosis is preferred)
2. date/time of onset
3. date/time of resolution
4. severity (mild, moderate, severe)
5. causality (unrelated, doubtful/unlikely, possible, probable, definite)\*
6. seriousness (yes, no)
7. action taken (with regard to IP/study drug)
8. other action (to treat the event)
9. outcome and sequel (follow-up on AE)

\*Causality assessment will be made only when the AE occurs after the subject has initiated at least one infusion of the IP/study drug. An AE occurring before subject's exposure to IP/study drug will be always labeled as "unrelated".

For AEs that occur during infusions, the infusion rate in effect at the time of onset of the AE, the time of onset of the AE and the time of AE change materially in intensity and/or resolve will be captured in the eCRF.

In addition to the Investigator's own description of the AEs, each AE will be encoded according to the Medical Dictionary for Regulatory Activities (MedDRA).

For example, a laboratory test abnormality considered clinically relevant, eg, causing the subject to withdraw from the study, requiring treatment or causing apparent clinical

manifestations, or judged relevant by the Investigator, should be reported as an AE. Each event must be described in detail along with start and stop dates, severity, relationship to IP/study drug, action taken, and outcome. Each event must be adequately supported by documentation as it appears in the subject's medical or case file.

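### Doubtful/Unlikely borrows Probable's criterion, so a well-timed, unexplained event without dechallenge is graded below the same event with another possible cause

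*Protocol*

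**What the plan says.** Protocol Section 4.3.3 has the investigator grade every AE against five definitions:

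- **Definite:** plausible timing (or a measured treatment level), confirmed by dechallenge and by rechallenge. Dechallenge is explained as "improvement on stopping the treatment (dechallenge").
- **Probable:** plausible timing, for an event "that is confirmed by dechallenge; and that could not be reasonably explained by the known characteristics" of the clinical state.
- **Possible:** plausible timing, for an event that might have come from the subject's "clinical state or other modes of therapy administered to the subject". Dechallenge is not mentioned.
- **Doubtful/Unlikely:** worded as "An event that follows a reasonable temporal sequence from administration of the treatment; but that could not be reasonably explained by the known characteristics", again with reference to clinical state. Dechallenge is not mentioned.
- **Unrelated:** whatever fits none of these.

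The same section rules out the Unrelated label "when a causal relationship between the study treatment and the AE cannot be ruled out by the Investigator and/or Sponsor". It counts probable, possible and doubtful/unlikely events alike as suspected ADRs.

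Section 4.3.7 gives the order of the scale for the eCRF: "causality (unrelated, doubtful/unlikely, possible, probable, definite").

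The stopping rule in Section 3.9 has two steps. Five subjects on IGSC 20% with an SAE of the same preferred term (infections and documented underlying disorders excepted) lead the sponsor to form a Safety Review Committee (SRC). Then, where the clustering is medically plausible and the SAEs are graded definitely, probably or possibly related "by both the Investigator and the SRC, consideration would be given to possibly discontinuing the study".

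**The concern.** A causality scale should rise, or at least not fall, as competing explanations for an event become weaker. The lowest suspected grade here uses the clause that makes Probable incriminating. The word that introduces the clause in the Doubtful/Unlikely definition signals a contrast, so a contrary condition was probably intended; this is an inference from the wording.

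Two things are at stake. First, an investigator who follows the text would give a lower grade to the event for which the study drug is the only candidate cause. Second, step two of the stopping rule leaves out Doubtful/Unlikely. Read literally, a well-timed, unexplained SAE without dechallenge would not meet that step, while one with an alternative cause would.

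The affected profile is not contrived. Under Section 4.3.6 an event is serious if, "in the view of either the Investigator or Sponsor, it results in any of the following outcomes", and the first outcome listed is death. A fatal event cannot show improvement after treatment is stopped, so it can never have dechallenge as Section 4.3.3 defines it. A well-timed, otherwise unexplained death would be Doubtful/Unlikely, and a death that the clinical state could have produced would be Possible.

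**Working it through.** The protocol gives no figure to reproduce, so the check applies its definitions to every kind of well-timed event.

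**Inputs.** The five definitions come from Section 4.3.3 and the ranking from Section 4.3.7. One assumption is added: where an event meets several grades, the highest applies. The protocol does not say this, but without it an unexplained event with dechallenge would meet both Probable and Doubtful/Unlikely.

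**Profiles.** Timing is plausible throughout. The rows are the dechallenge evidence. The columns are the strength of the competing explanation:

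- A: not explained, and no other conceivable cause
- B: not reasonably explained by the clinical state, but clinical state or other therapy could have contributed
- C: reasonably explained by the clinical state

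**As written:**

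| | A | B | C |
|---|---|---|---|
| No dechallenge | Doubtful/Unlikely | Possible | Possible |
| Dechallenge only | Probable | Probable | Possible |
| Dechallenge and rechallenge | Definite | Definite | Definite |

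The first cell is the one that matters. Without dechallenge the event fails Definite and Probable. Without another conceivable cause it fails Possible. Only Doubtful/Unlikely is left.

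**Count.** Each row allows three comparisons (A with B, A with C, B with C), so 3 rows × 3 = 9. The less explained event gets the lower grade in:

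- no dechallenge: A against B and A against C, so 2
- dechallenge only: 0
- dechallenge and rechallenge: 0

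The total is 2 of 9 comparisons, both caused by 1 of the 9 profiles.

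**With *not* deleted from the Doubtful/Unlikely definition:**

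| | A | B | C |
|---|---|---|---|
| No dechallenge | Unrelated | Possible | Possible |
| Dechallenge only | Probable | Probable | Possible |
| Dechallenge and rechallenge | Definite | Definite | Definite |

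The inversions remain at 2 of 9. The affected profile now meets no named grade and drops to Unrelated, a label that Section 4.3.3 itself forbids when causality cannot be ruled out. No cell is left at Doubtful/Unlikely either, because a reasonably explained event also meets Possible. The obvious one-word edit therefore does not repair the scale.

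**The case against.** The strongest counter-argument is that the prose is not the only tool. Section 4.3.3 also says that the operational decision rests on published algorithms, which may steer an assessor away from the literal reading. That is a fair limit on how many events would be misgraded in practice. But the algorithms are cited and not reproduced, the section says assessment will follow its definitions, and nothing in the algorithms corrects the text.

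The link to the stopping rule is also remote. Step one and the formation of the SRC need no causality grade, the SRC makes its own designation, step two is discretionary, and Section 3.9 allows the study to be closed in any case. Suspected-ADR summaries do not change between Possible and Doubtful/Unlikely, and Section 4.4.1 requires SAE reporting regardless of attribution. All of this stands and limits the severity. It does not make the definition right.

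The profile is narrow, since Possible is easy to meet, and the protocol gives no count of such events. The ninths come from a grid built for this check, and its no-dechallenge row combines dechallenge that was not done with dechallenge that failed. The figures describe the structure of the scale and say nothing about event frequency.

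Finally, it can be said that Possible grades are the same as written and with *not* deleted, so re-checking them is unnecessary. That does not hold: a properly corrected lower grade could take in events now graded Possible.

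**Conclusion.** The definition is wrong as written. It reads as a drafting error rather than a design decision, and it should be fixed. One profile, a well-timed event with no confirmed dechallenge and no other conceivable cause, is graded below the same event with a competing explanation. On the grid above that is 1 of 9 profiles and 2 of 9 comparisons.

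The conclusion rests on reading Section 4.3.3 literally. The count also rests on the assumption that the highest grade met applies. The inversion itself does not need that assumption: the affected profile meets only Doubtful/Unlikely, and a reasonably explained event without dechallenge meets only Possible.

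The practical reach is limited to the recorded grade and to step two of the stopping rule. The primary PK analysis is untouched. How many events would be affected cannot be determined from the protocol.

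**What to change.** Rewrite the Doubtful/Unlikely definition in Section 4.3.3 so that two conditions hold: the grades are ordered, and a well-timed, unexplained event without dechallenge information neither ranks below an explained one nor falls to Unrelated. State that the highest grade met applies. The boundary with Possible needs attention at the same time, since deleting *not* alone fails.

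Reconcile the corrected grades with the scale in Section 4.3.7 and with the grades named in the Section 3.9 stopping rule. The sponsor should choose the wording; no stopping criterion is proposed here.

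The cost is a short text correction, a site memo with eCRF guidance, and a re-check of events already graded possible or doubtful/unlikely. No new data collection is needed.

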#### 4.3.4 Severity of Adverse Event or Suspected Adverse Drug Reaction

AEs and suspected ADRs will be classified depending on their severity according to the following definitions:

1. Mild: an AE which is well tolerated by the subject, causing minimum degree of malaise and without affecting normal activities.
2. Moderate: an AE that interferes with the subject’s normal activities.
3. Severe: an AE that prevents the subject from performing their normal activities.

AE and suspected ADR severity gradation must be distinguished from AE and suspected ADR seriousness gradation, which is defined according to event consequence. For example, headache can be mild, moderate or severe but not necessarily serious in all these cases.

The Investigator will be responsible for assessing the AE and suspected ADR intensity during the clinical trial, taking into account current criteria included in this section.

#### 4.3.5 Expectedness of Adverse Event or Suspected Adverse Drug Reaction

An AE or suspected ADR is considered “unexpected” if the nature, seriousness, severity or outcome of the reaction(s) is not consistent with the reference information. The expectedness of an AR shall be determined by the Sponsor according to the reference document (ie, IB).

Events not listed for the particular drug under investigation in the IB are considered “unexpected” and those listed are considered “expected.” When new Serious ADRs (potentially related SAEs) are received, it is the Sponsor’s responsibility to determine whether the events are “unexpected” for expedited safety reporting purposes.

#### 4.3.6 Seriousness of Adverse Event or Suspected Adverse Drug Reaction; Serious Adverse Event

An AE or suspected ADR is considered “serious” if, in the view of either the Investigator or Sponsor, it results in any of the following outcomes:

1. Death
2. Life-threatening AE (life-threatening in the definition of “serious” refers to an event in which the subject was at risk of death at the time of the event; it does not refer to an event which hypothetically might have caused death if it were more severe)
3. In-patient hospitalization or prolongation of existing hospitalization
4. A persistent or significant incapacity or substantial disruption of the ability to conduct normal life functions
5. A congenital anomaly/birth defect
6. An important medical event (important medical event in the definition of “serious” refers to those events which may not be immediately life-threatening, or result in death, or hospitalization, but from medical and scientific judgment may jeopardize the subject or/and may require medical or surgical intervention to prevent one of the other outcomes listed above).

This definition permits either the Sponsor or the Investigator to decide whether an event is “serious”. If either the Sponsor or the Investigator believes that the event is serious, the event must be considered “serious” and evaluated by the Sponsor for expedited reporting.

A distinction should be drawn between serious and severe AEs. The term “severe” is used to describe the intensity (severity) of a specific event; the event itself, however, may be of relative minor medical significance (such as severe headache). This is not the same as “serious”, which is defined on subject/event outcome or action criteria usually associated

with events that pose a threat to a subject's life or functioning. Seriousness (not severity) is a medical term while severity is a subjective term.

According to the medical criteria, an AE or a suspected ADR can be classified as serious, although it does not fulfill the conditions fixed in this section, if it is considered important from a medical point of view.

#### 4.3.7 Adverse Event and Pregnancy Documentation

All AEs and SAEs occurring after the subject has signed the ICF through the Final Visit (ie, end of study) must be fully recorded in the subject's eCRF or SAE form and medical record. If no AE has occurred during the study period, this should also be indicated in the eCRF.

It is the responsibility of the Investigator to ensure that AEs are appropriately recorded.

At each visit, AEs will be elicited by asking the individual a non-leading question such as "Do you feel different in any way since the last visit?" Moreover, AEs will also be collected through directly observed events or spontaneously volunteered by the subject. Clearly related signs, symptoms and abnormal diagnostic procedures should preferably be grouped together and recorded as a single diagnosis or syndrome wherever possible.

The following variables must be recorded in the AE eCRF:

1. the verbatim term (a diagnosis is preferred)
2. date/time of onset
3. date/time of resolution
4. severity (mild, moderate, severe)
5. causality (unrelated, doubtful/unlikely, possible, probable, definite)\*
6. seriousness (yes, no)
7. action taken (with regard to IP/study drug)
8. other action (to treat the event)
9. outcome and sequel (follow-up on AE)

\*Causality assessment will be made only when the AE occurs after the subject has initiated at least one infusion of the IP/study drug. An AE occurring before subject's exposure to IP/study drug will be always labeled as "unrelated".

For AEs that occur during infusions, the infusion rate in effect at the time of onset of the AE, the time of onset of the AE and the time of AE change materially in intensity and/or resolve will be captured in the eCRF.

In addition to the Investigator's own description of the AEs, each AE will be encoded according to the Medical Dictionary for Regulatory Activities (MedDRA).

For example, a laboratory test abnormality considered clinically relevant, eg, causing the subject to withdraw from the study, requiring treatment or causing apparent clinical

manifestations, or judged relevant by the Investigator, should be reported as an AE. Each event must be described in detail along with start and stop dates, severity, relationship to IP/study drug, action taken, and outcome. Each event must be adequately supported by documentation as it appears in the subject's medical or case file.

A pregnancy not verified before the screening visit but occurring during the course of the study will not be considered an AE unless a relation to the study drug is at least suspected. In any case, a Pregnancy Report Form must be completed and sent within 24 hours to the Sponsor, and the study treatment must be discontinued. A copy of the form should be filed at the study site for follow-up until the end of the pregnancy.

